The obstetrical population is considered vulnerable. Pregnancy involves multiple interactions with the health care system and eventually all are admitted to the hospital for delivery, therefore, managing pregnant population presents a unique challenge during this pandemic. Additionally, the physiological changes and partial immune suppression during pregnancy makes the pregnant women and newborn babies susceptible to several infections. Post-partum hemorrhage, maternal sepsis, preeclampsia, premature rupture of membrane are the most common adverse events reported to have caused by this disease in pregnant women (11).

There are currently limited data on fCOVID-19 infections during pregnancy. Anecdotal evidence suggests that pregnant women do not appear to be different than the general population in terms of disease transmission. In addition, neonatal vertical transmission has been suspected in a neonate of a COVID-19 positive mother (12). Recently, poor maternal and neonatal outcomes including critical care admission, preterm normal and cesarean delivery, premature rupture of the membrane or PROM , fetal distress, stillbirth, and multiple organ dysfunction (1,11,13-17).

Importance of Registry

From the limited information gathered about the novel coronavirus, its impact on pregnancy and newborn and the drastically increasing burden of the disease, it is vital that scientific information concerning the disease is collected and shared in a concise and practical manner. Hence, there is a need to collect case data rapidly, to pool global data on the natural history of women affected by suspected COVID-19 or confirmed SARS-CoV-2 in pregnancy to inform treatment and implement preventative strategies in this and future outbreaks. A centre-based registry, gathering case data prospectively on the effect of SARS-CoV-2 infection from healthcare systems around the world offers a method to accrue clinical outcomes on key research questions from a variety of populations and the Q-PRECIOS register will serve such purpose.

4. Objectives

In this section provide a clear statement of the primary and any secondary objectives of the study

The main aim of this study is to understand the natural course of the COVID-19 infection during pregnancy and postnatal period. To this end the registry objective are to:

1. To form a disease registry linked with other national data sources for women with suspected COVID-19 or confirmed SARS-CoV-2 in pregnancy and their neonates.

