 - 1.1 Study the course of COVID-19 disease i.e. its symptoms, duration, progression in pregnant women
 - 1.2 Study the pregnancy, postnatal and neonatal effect of COVID-19 disease

Objective justification

The in-utero exposure of acute viral infection in some instances is proven to have short- and long-term neonatal effect during the postnatal and childhood period and the Zika virus, measles, mumps and rubella are few examples. COVID-19 is caused by a novel coronavirus strain of unknown consequences. The main purpose of this registry is to collect a baseline data and help establishing future studies and hypothesis generation.

In addition, we will be exploring the psychological impact of COVID-19 on women during the pregnancy and postnatal period. Stress and anxiety level are increased with potential adverse pregnancy and/or neonatal outcomes especially during infectious disease outbreak. In fact, COVID-19 is associated with adverse maternal and neonatal outcomes resulting in increased level of stress and anxiety. In addition, women during the pregnancy, peripartum, and postpartum period are at increased risk of depression. A risk that has been aggravated by social and physical isolation. Indeed, the social and physical isolation, a critically needed measure to stop the virus transmission, resulted in increased stress and depression level and adversely affecting the mental and physical health of both the mother and the baby.

5. Indicate if this is a retrospective data review

- **Retrospective Chart/data Review**
- **Provide the date range of the chart review**

6. Study Methodology

This is a nationwide prospective observational registry linked with PAN-COVID UK register of pregnant women with suspected and/or confirmed diagnosis of COVID-19 infection. The enrollment period for this registry is 2 years e.g. May 1, 2020 to May 1st, 2022. Case reports or cases diagnosed ever since 27th Feb will also be included. The authors of published case reports will be contacted for permission. This registry will open for enrollment after IRB/MRC approval. Understanding the effect of COVID-19 infection on pregnancy and its outcome is imperative to help the patients and healthcare providers understand the impact of the disease on the pregnant women and their offspring. There is no intervention planned in this study, therefore, there is a minimal risk associated with this study.

Data collection:

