We will also contact corresponding authors of case reports of women with COVID-19 from February 2020 for their written consent, by email, for inclusion of the data from these reports in the PAN-COVID register.

Sample size calculation:

Based on a recently published study, 15% of pregnant women were SARS-CoV-2 positive. Out of which only 12% (1.9% of total study patients) were symptomatic. The total number of deliveries per year in Qatar is between 19000 – 21000 deliveries (1650 patients/month). Diagnosis of COVID-19 in Qatar is based on selective criteria i.e. presenting with symptoms, recent travel to endemic area or contact with a confirmed case. However, all women undergoing cesarean section are screened. Therefore and based on 95% CI and 0.05 margin of error, we anticipate a total 170 - 200 case per month.

8. Study procedures

Study Duration and Timelines

This registry is expected to enroll patients for 2 years and follow them up to 1 year postnatally i.e. the registry duration will approximately last for 4 years.

Study timeline:

Patient enrollment: 2 years

Data collection and curation: 4 years

Study visit numbers: 7-10 visits ([see details below](#)); Initial patient visit is expected to last for 30 minutes.

1. [baseline,](#)
2. [weekly for 4 weeks,](#)
3. [At 24 – 34 – 36 – 38 weeks of gestation \(provided that baseline and the 4 weekly follow up occurred earlier\),](#)
4. [At 6 weeks, 6 and 12 months postpartum \(for both mother and the baby\)](#)

[Further to that, the first visit “baseline” will be collected by the primary physician who is taking care of the participating patient. All subsequent visits will be over the phone with mother.](#) Telephone calls for follow up visit are expected to last 15 – 30 minutes.

Data analysis: interim and final

Final report: 2 months

Study procedure:

Suspected patient or patients with positive COVID results will be identified through Cerner. Patients will then be contacted through the primary physician to explain the study and obtain consent forms once accepted. The primary physician will then collect demographic and baseline data after obtaining patient consent (appendix 1 & 2). Apart from the initial visit, there is no anticipated future study visits. Data collection will be either through the phone or using a self-administered survey that will be sent through SMS.

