Once the laboratory result is confirmed and verbal consent is obtained, patient details will be entered into the online study database and given a study number.

Risk

The is a prospective observational registry. There minimal risk of breach of patient confidentiality. To minimize this risk, data will be entered into an electronic registry software. The software will be secured with username and password and only accessible by the study investigators for data entry. Data extraction will only be accessible to study PIs and co-PIs. Paper based data collection sheet will be secured in locked cabinets accessible only by study PIs and co-PIs. Only de-identified data will be shared amongst investigators. If a breach in confidentiality occurs, the IRB will be notified immediately. Consent form containing the linking information between collected data and patient's identifiable information will be stored in a locked cabinet and/or password locked computer. Information on the password protected computer database will only be accessed by the investigators. Furthermore, the PI's office will remain locked. All study documentation will be stored according to the MRC guidelines

Bio-Specimens & Sample Collection

NA

Outcomes

We believe the results of this study will generate robust data. Prevalence of SARS-CoV-19 infection in pregnancy. Percentage and distribution of COVID-19 presenting sign and symptoms. Percentage of adverse pregnancy and neonatal outcomes. Description of mental status of pregnant women affected by COVID-19 infections.

Data Collection, Management & Confidentiality

a) Indicate below HOW study data will be collected for the proposed research.

Study Forms Study Database Study Web-Based/App Other

Please detail how study data will be coded:

Once informed consent is obtained, patient will be given study number and entered in the registry system. Data will be stored registry database/web-portal password protected on Cerner. Only study investigators have access for data entry. For follow up purposes, study investigators will have access to the identifiable information during the data collection period. No individual identity will be disclosed in results and publications.

b) Describe below WHERE and HOW the study data is physically stored.

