Data collection/entry: HMC physicians will be eligible to enter patient initial assessment form. Follow up data study investigators and research coordinators will have access to enter patient data into the database.

Data extraction for audit, analysis, report and request of collaboration:

Data extraction access will be granted to specified personnel designated by the register steering committee.

e) Describe below HOW the study data is accessed.

Level access will be employed from HMC Cerner team. Study data will be accessed using a dedicated username and password for specified members.

f) Will subject identifiers be shared outside of HMC? If YES describe below WHOM the study data is shared

No, only deidentified data will be shared.

Subject Withdrawal/ Withdrawal of Consent

In case patient wish to be withdrawn from the study, no further contact will be made. However, collected information up to the point of withdrawal will be included in the analysis. Subjects withdraw from the study will be asked whether they are willing to allow ongoing data collection and his response will be recorded.

9. Statistical Consideration and Data Analysis

Descriptive data: Numerical data will be presented as mean and standard deviation where normally distributed or median and range where it's not normally distributed. Categorical data

will be presented as frequency and percentages. Prevalence of COVID-19 will be calculated as total number of patients who were positive over total number deliveries in the same month. Inferential analysis will be used to assess association and tests will be selected according to suitability.

10. Adverse Event Reporting

This is an observation study. There are no anticipated adverse events.

11. Ethical Consideration.

The registry will only commence after obtaining approval from IRB/HMC in accordance with good clinical practice, and MoPH regulations

12. Sponsor, Funding & Collaborator Information

MRC

13. Dissemination of Results and Publication policy

Once the project is funded, the study team will initiate monthly meetings to discuss study plans and patient recruitment. Team leaders will also meet monthly to share study updates. Furthermore, the study results will be shared among peers in the department through presentation of study findings. Finally, once the study is completed, we aim to present our findings at the Hamad Medical Corporation Annual Research Day, local and international conferences and in peer-reviewed journals.

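### The overall symptomatic percentage will partly reflect who was tested, and the plan does not split it by reason for testing

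*Combined protocol and SAP*

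**What the plan says.** The sample size text in section 7 states that diagnosis in Qatar is "based on selective criteria i.e. presenting with symptoms, recent travel to endemic area or contact with a confirmed case". It then adds: "However, all women undergoing cesarean section are screened". The same paragraph cites a published study in which 15% of pregnant women were positive: "Out of which only 12% (1.9% of total study patients) were symptomatic".

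Section 8 (Outcomes) lists "Percentage and distribution of COVID-19 presenting sign and symptoms. Percentage of adverse pregnancy and neonatal outcomes". Section 9 says that categorical data "will be presented as frequency and percentages", and on association says only: "Inferential analysis will be used to assess association and tests will be selected according to suitability". Neither section names the reason for testing as a split, a restriction or a covariate, and neither gives the denominator of the symptom percentages.

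Women can enter in several ways. Section 7 includes suspected as well as confirmed infection, whereas the eligibility screening text in section 8 requires a positive PCR. Section 8 (Informed Consent) allows self-referral through posters and social media. Section 6 also admits published case reports. Enrolment runs for two years.

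**The concern.** Symptoms are both a reason for being tested and the result to be reported. Women with symptoms are tested because of them. Women without symptoms are tested only if they have a travel or contact history or are having a caesarean. If asymptomatic infections outside the caesarean group are missed more often than symptomatic ones, the share of registered women with symptoms is pushed upward.

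Two things are at stake. First, the overall percentage could be read as a feature of the disease in pregnancy when part of it is a feature of local testing. Section 4 says the registry is to supply baseline data for later studies, which would inherit the figure. Second, if contact tracing, travel testing or screening changes during enrolment, the percentage would move with no change in the disease. A pooled table gives the reader no means of telling the two apart.

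**Working it through.** **The plan's own figure.** 12% × 15% = 1.8%, and 1.9 / 15 = 12.7%. The stated 12% and 1.9% agree within rounding. The 170-200 cases per month is not an input here.

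**Inputs to the illustration**
- s = true symptomatic share, 0.12 (section 7, from the cited study; taken as true for illustration).
- c = caesarean rate: not in the documents; assumed 0.20, 0.30 or 0.40.
- f = share of asymptomatic infections outside the caesarean group that are found (by contact or travel testing): not in the documents; varied.
- Further assumptions: every symptomatic woman and every caesarean is tested, symptoms are unrelated to mode of delivery, and infections are detectable at delivery.

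**Formula.** All symptomatic infections are found. Of the asymptomatic ones, the fraction c + (1 − c)f is found. So

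observed share = s / [s + (1 − s)(c + (1 − c)f)].

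**Results**

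| f | c = 0.20 | c = 0.30 | c = 0.40 |
|---|---|---|---|
| 1 (all found) | 12% | 12% | 12% |
| 0.5 | 0.12/0.648 = 18.5% | 0.12/0.692 = 17.3% | 0.12/0.736 = 16.3% |
| 0 (none found; limit) | 0.12/0.296 = 40.5% | 0.12/0.384 = 31.3% | 0.12/0.472 = 25.4% |

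**Change in testing over time.** At c = 0.30, f = 0.25 gives 0.12/0.538 = 22.3% and f = 0.75 gives 0.12/0.846 = 14.2%. The underlying share is 12% in both.

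**The detectability assumption.** Section 7 enrols throughout pregnancy and up to six weeks after delivery, and a test at caesarean does not find an infection that has already cleared. In the formula this acts as a smaller c. At the extreme c = 0 with f = 0.5, the share is 0.12/(0.12 + 0.88 × 0.5) = 0.12/0.56 = 21.4%.

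**The caesarean-screened group.** It is not a clean reference. If symptomatic women were 1.5 times as likely to have a caesarean (assumed), its share would be 0.18/(0.18 + 0.88) = 17.0%. If half of the symptomatic women had been diagnosed earlier and counted elsewhere (assumed), it would be 0.06/(0.06 + 0.88) = 6.4%. The first is not far-fetched: the background section lists "preterm normal and cesarean delivery" among the poor outcomes reported with the infection.

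**The case against.** The strongest reply is that the plan never promises to estimate the symptomatic share of all infections. It describes registered cases, and the 12% is only an input from a cited study. That is fair, and it limits the point. The distribution of signs among symptomatic women does not change when asymptomatic infections are missed. What moves is any percentage taken over all registered women, and the plan neither rules out that denominator nor attaches a caution to it.

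A reader might infer from the table that the figure could be inflated to 25-41%. The documents do not support that as an expectation. Those values need no asymptomatic infection to be found outside caesarean, whereas section 7 says contacts and travellers are tested and includes quarantine sites. They are a limit. A reader might also infer a bias of known direction in the preterm or neonatal percentages; nothing in the documents gives its size or direction.

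A further reply is that the appendix forms are listed by title only, so the reason for testing may already be collected. That stands for the form, but not for the analysis, since section 9 names no such split. Its open wording on choice of tests would permit one but does not plan it, and concerns association rather than the descriptive percentages.

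Finally, testing is not the only selection. Suspected cases, self-referrals and published case reports may also be selected on symptoms or severity. This stands, and a split by testing route alone would not deal with it.

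**Conclusion.** The point holds for the overall symptomatic percentage. Followed as written, the plan gives a pooled figure that depends partly on testing practice, and no other section corrects this. The direction is upward, provided asymptomatic infections outside the caesarean group are missed more often than symptomatic ones.

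The size cannot be computed from the documents, which give neither the caesarean rate nor the share of other asymptomatic infections found. The illustrative 16-19% against 12% is neither an estimate nor a bound. It rests on half of those infections being found, a caesarean rate of 20-40%, complete testing of symptomatic women and caesareans, no link between symptoms and mode of delivery, and detectability at delivery. The last of these fits poorly with enrolment throughout pregnancy.

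This concerns how one descriptive outcome is reported and read. It does not undermine the registry.

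**What to change.** 1. Confirm that the baseline form records the reason for testing (symptoms, travel, contact, pre-caesarean screen; more than one allowed) and the route into the registry (including suspected without PCR, self-referral and published case report). Add the fields if they are missing.
2. In section 9, plan symptom percentages by testing route beside the overall figure, with published case reports shown separately, and state the denominator of each percentage.
3. State with the results that the overall figure depends on testing practice, and that the caesarean-screened group is itself selected: illness may lead to caesarean, and women diagnosed earlier may be absent from it.

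The cost is at most a few form fields, one set of split tables and a short statement. The milestone table in section 8 shows building the Cerner forms as a step in the work plan, so the fields are cheapest to settle before that build.

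The downside is smaller subgroups. For ±5 points around 12%, 1.96² × 0.12 × 0.88 / 0.05² = 162.3, so 163 women are needed. With section 7's 1650 deliveries a month, an assumed positivity at delivery of 5-15% (15% is section 7's figure) and a caesarean rate of 20-40%, the screened group gains between 1650 × 0.05 × 0.20 = 16.5 and 1650 × 0.15 × 0.40 = 99 women a month. It would reach 163 in about 1.6 to 9.9 months if all were enrolled, and later if not. The 1650 is a national count, so this is an optimistic guide.

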Objective 1: To form a disease registry **linked with other national data sources** for women with suspected COVID-19 or confirmed SARS-CoV-2 in pregnancy and their neonates.

Objective 1.1: Study the course of COVID-19 disease i.e. its symptoms, duration, progression in pregnant women

Objective 1.2: Study the pregnancy and neonatal effect of COVID-19 disease

We will collect information about patient demographic, co-morbidities, clinicopathological information, COVID-19 disease sign, symptoms and its treatment, pregnancy and neonatal outcomes, and women mental health during pregnancy and postnatal period. Regarding pregnancy outcomes, our study will focus on miscarriage, fetal growth restriction and stillbirth, pre-term delivery and vertical transmission and will include fields on ultrasound diagnosis and neonatal care (for details refer to appendix 1, 2 and 3). The woman and her neonate(s) will be followed for 1 year postnatally. Regarding the neonatal outcomes, outlined in the neonatal outcome data collection sheet, includes birth weight, congenital malformations, APGAR score, Breastfeeding, COVID-19 status, respiratory symptoms, neonatal status, and discharge status.

Baseline characteristic and initial assessment will be done during the hospital admission up on COVID-19 diagnosis. Apart from that, there are 7-10 expected follow up telephone calls or online forms to be sent to the patient. The schedule and timeline of data/biospecimen collection are described in table 1.

Data Collection Form or Questionnaire	Baseline	Weekly for 4 weeks	2 nd Trimester (GA 24 weeks)	3 rd Trimester (GA 34 weeks)	GA 36 weeks	GA 38 weeks	6 weeks postpartum	6 Months	12 Months
Demographics, Health History and COVID-19 Questions	X								
COVID-19 Symptoms Follow-up		X	X	X			X	X	X
Pregnancy Status/Outcomes		X	X	X	X	X	X		
Depression and Anxiety*	X		X	X			X	X	X
Neonatal/Infant Outcomes							X	X	X

*Generalized Anxiety Disorder 7-item (GAD-7) scale and Edinburgh Postnatal Depression Scale (EPDS)

7. Study Population and Study Setting/ Location

We will include all pregnant patients with suspected or confirmed COVID-19 infection at all HMC facilities including WWRC, CH, AKH, AWH and its associated quarantine sites and their offspring's. The inclusion criteria are:

1. pregnant woman with suspected or confirmed SARS-CoV-2 infection
2. postpartum women who delivered during the last six weeks and
3. neonate(s) of women included in the registry.

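### Routine caesarean screening over-represents caesarean births in the registry, so crude preterm, growth-restriction and neonatal-care percentages are likely inflated, by an uncertain amount

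*Combined protocol and SAP*

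**What the plan says.** - **Testing (Section 7, sample size calculation).** "Diagnosis of COVID-19 in Qatar is based on selective criteria i.e. presenting with symptoms, recent travel to endemic area or contact with a confirmed case". The next sentence adds the exception: "However, all women undergoing cesarean section are screened". The expected accrual is then presented as following from these statements.
- **Case finding (Section 8, study procedure).** "Suspected patient or patients with positive COVID results will be identified through Cerner". The eligibility screen under Informed Consent is a positive PCR. Neither place asks why the test was done.
- **Timing of entry (Sections 6 and 7).** Baseline takes place at the hospital admission when COVID-19 is diagnosed, and women up to six weeks postpartum are eligible. Entry at or after delivery is therefore expected.
- **Outcomes (Section 6, data collection).** "our study will focus on miscarriage, fetal growth restriction and stillbirth, pre-term delivery and vertical transmission". The Outcomes part of Section 8 promises percentages of adverse pregnancy and neonatal outcomes.
- **Analysis (Section 9).** Descriptive summaries, plus tests of association to be chosen later. Nothing separates cases by reason for testing, time of detection or mode of delivery.

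**The concern.** An infected woman with no symptoms, travel or known contact is found if she delivers by caesarean and is generally missed if she delivers vaginally. Fetal compromise and growth restriction can be reasons for a caesarean, so the extra women brought in by this route may well have more of the outcomes that the registry counts. For them, gestation at delivery and fetal growth were also largely settled by the time the infection was found.

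Objective 1.2 asks for the effect of COVID-19 on pregnancy and the neonate. A crude percentage over all registered women would credit to infection part of what belongs to the selection of caesarean births. A larger registry would not cure this; it would only narrow the interval around a shifted value.

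**Working it through.** **The plan's own figures.** Section 7 takes 1650 deliveries a month and states that "15% of pregnant women were SARS-CoV-2 positive". It continues: "Out of which only 12% (1.9% of total study patients) were symptomatic" (0.12 × 0.15 = 1.8%, close to the stated 1.9%). It concludes: "based on 95% CI and 0.05 margin of error, we anticipate a total 170 - 200 case per month".
- Accrual at 15%: 0.15 × 1650 = 247.5 a month. At 1.9%: 31 a month. Neither gives 170-200.
- Single-proportion precision: 1.96² × 0.15 × 0.85 / 0.05² = 196. This lies in the range, but it is a required sample size and not a monthly count.

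So 170-200 does not reproduce as an accrual figure. It is used below only as the plan's stated expectation.

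**Detection gap.** Among women delivering, 15% are found positive under universal screening, against 1.8% on symptoms alone. That is about eightfold, and less once contact and travel testing count. Caesareans are over-represented whenever detection elsewhere is below 15%.

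**Illustration with no effect of infection.** From the plan, per month: 247.5 positive, of whom 0.12 × 247.5 = 29.7 symptomatic and 217.8 asymptomatic. Assumed: caesarean rate c = 30%, preterm risk 18% with caesarean and 7% without. Let d be the share of asymptomatic vaginal deliveries that are detected.

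- True preterm percentage: 0.3 × 18 + 0.7 × 7 = 10.3%.
- Asymptomatic caesareans: 0.3 × 217.8 = 65.34. Asymptomatic vaginal deliveries: 152.46.
- Registered cases: 29.7 + 65.34 + 152.46d.
- Preterm cases: 29.7 × 0.103 + 65.34 × 0.18 + 152.46d × 0.07 = 14.82 + 10.67d.

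| d | Cases per month | Registry preterm % | Ratio to 10.3% |
|---|---|---|---|
| 0 | 95 | 15.6 | 1.51 |
| 0.25 | 133 | 13.1 | 1.27 |
| 0.49 | 170 | 11.8 | 1.15 |
| 0.50 | 171 | 11.8 | 1.14 |
| 0.69 | 200 | 11.1 | 1.08 |

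The 170 and 200 rows solve for d: (170 − 95.04)/152.46 = 0.49 and (200 − 95.04)/152.46 = 0.69. With c from 20% to 40% and d from 0 to 0.5, the ratio runs from 1.13 to 1.57.

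**Sensitivity to the outcome ratio.** Let RR be the outcome risk with caesarean divided by that without, and s the caesarean share of registered cases. The inflation factor is (s·RR + 1 − s)/(c·RR + 1 − c). With c = 30% and symptom-only detection elsewhere (1.8%), s = 0.045/(0.045 + 0.0126) = 0.781.
- RR = 1.5, 2, 3: factors 1.21, 1.37, 1.60.
- RR = 1: no inflation. RR = 0.8: factor 0.90, a deflation.
- With 10% detection elsewhere, the factors at RR = 1.5, 2, 3 fall to 1.04, 1.07, 1.11.

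**Dilution by antenatal cases.** Women found during pregnancy through symptoms, travel or contact enter independently of delivery mode. If they are half of the registry, s = 0.5 × 0.30 + 0.5 × 0.781 = 0.541, and at RR = 2 the factor falls from 1.37 to 1.541/1.3 = 1.19. At three quarters, s = 0.420 and the factor is 1.09.

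**The case against.** The strongest reply is that the size, and even the direction, rests on figures the documents do not contain. This stands. No caesarean rate or outcome rate by delivery mode is given, and without an excess of the outcome among caesareans there is no inflation. Only preterm delivery has been worked through above; growth restriction and neonatal care rest on the same reasoning, and no direction is shown for stillbirth.

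The 15.6% case also sits badly with the plan. It requires that travel and contact testing find no asymptomatic vaginal deliveries, and it yields about 95 cases a month against the 170-200 expected. Enrolment from the first trimester weakens the effect further.

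Three stronger readings are tempting, and the documents do not support them:
- A reader might infer that the adverse outcome itself drives entry. Caesarean drives entry; the outcome matters only as far as it leads to caesarean.
- A reader might infer that symptomatic-versus-asymptomatic comparisons are biased because asymptomatic cases are largely caesareans. Section 9 names no such comparison, and at d = 0.5 and c = 30% the caesarean share of asymptomatic cases is 65.34/(65.34 + 76.23) = 46%.
- A reader might conclude that outcome percentages should be restricted to women positive before the delivery admission. That would drop women admitted with COVID-19 who deliver during that stay, which biases towards no effect. It could also retain planned caesareans swabbed before admission, since the plan does not say when screening happens.

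The registry's hypothesis-generating purpose softens the matter but does not remove it: the protocol also expects robust data that help patients and providers understand the impact of the disease. The appendix forms are not shown and may record the reason for testing, but Section 9 makes no use of it.

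**Conclusion.** The concern holds in conditional form. On the plan's own description, detection depends on delivery mode, caesarean births are over-represented, and nothing in Section 9 deals with this. Crude percentages of preterm delivery, growth restriction and neonatal care are likely inflated, provided that these outcomes are commoner with caesarean.

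At the assumed 30% caesarean rate and 18% versus 7% preterm risks, the shift is from 10.3% to about 11.1-11.8% when accrual matches the plan's expectation. The 15.6% figure is an upper case for those inputs. A larger share of antenatally detected women makes the shift smaller. It would go too far to say that the percentages are certainly inflated, or inflated by about half. The point merits a change to Section 9; it does not invalidate the registry.

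**What to change.** In Section 9:
1. Classify each case by the reason for the first positive test (routine caesarean screening, or symptoms, contact or travel), using recorded test reason, sample date and delivery date.
2. Report pregnancy and neonatal outcome percentages, and any tests of association, separately for the two groups. Make the group not found by caesarean screening the main result.
3. Keep women tested for symptoms, contact or travel in the main group even when they are diagnosed at the delivery admission.
4. Report gestational age at detection, and base preterm percentages on women first positive before 37 weeks. Women first positive later cannot deliver preterm and would pull the percentage down.
5. Retain caesarean-screen cases for neonatal infection status and postnatal follow-up.

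The cost is analysis wording, one extra field if the reason for testing is not already collected, and fewer women in the main outcome table. If contact and travel testing find the same share d of asymptomatic women in both delivery modes, the main group in the illustration is 29.7 + 217.8d. That is about 137 of 170 cases at d = 0.49 or 180 of 200 at d = 0.69, so intervals are wider by factors of about √(170/137) = 1.11 and √(200/180) = 1.05.
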